## 9.2. Recruitment Visit (Visit 1)

Once the subjects have agreed to participate in the study, they will be invited for the recruitment visit, when the following activities will be performed by the research team:

- written informed consent/assent
- checking inclusion and exclusion criteria
- medical (diabetes) history
- body weight and height measurement; calculation of BMI
- blood pressure measurement
- 12-lead electrocardiogram recording
- record of current insulin therapy
- record of occupation and educational attainment

**Austria only** - At the recruitment visit, the subject will have a breath alcohol test, a urine drug screen, and blood test for serology (HIV/Hepatitis B, C).

### 9.2.1. Screening blood sampling

Blood samples will be taken for the screening measurement of random C-peptide, glucose, and HbA1c. Liver, renal, thyroid function, full blood count, anti-transglutaminase antibodies and IgA will also be evaluated (if not done in previous 3 months). Less than 15 ml of whole blood will be taken from each participant.

### 9.2.2. Human factor assessments

Human factors assessment to understand expectations, attitudes, and behaviours that influence the uptake and response to using a closed-loop system will be undertaken at baseline. This will include surveys listed in Table 3. It is estimated that participants will take 20-25 minutes to complete surveys.

*Table 3. Human Factors Assessment Battery.*

Measure	Construct Measured / Relevant Points
WHO-5 quality of life measure*	All participants complete this 5 item measure from the World Health Organization (WHO) that assesses health related quality of life. (5 items; 3 mins)

Diabetes Distress Scale*	Gold standard measure for understanding distress symptoms related to diabetes. A recently validated version for adults with T1D includes 28 items and takes 6 minutes to complete.
Glucose Monitoring Satisfaction Survey*	This recently validated survey is an outgrowth of DirecNet and JDRF CGM surveys. It has been reduced to 15 items and evaluates treatment satisfaction and burden. (4 mins)
Hypoglycemia Confidence*	Includes 8 different common situations where hypoglycemia occurs (e.g., physical activity, driving) and evaluates level of confidence it can be managed in those situations. (8 items; 3 mins)
INSPIRE Survey	Newly developed measure of the psychosocial impact of closed-loop. Include 31 items and takes 5 - 7 minutes to complete.
Pittsburgh Sleep Quality Index (PSQI)	The PSQI is a validated 19 item questionnaire that holistically assesses sleep quality and sleep duration.
Cognitive Functioning	Computerised assessment of attention, executive functioning, and processing speed using standardised tools from CogState (10 – 12 minutes)

### **9.3. Training session on the use of the study insulin pump (Visit 2)**

This session will cover key aspects of insulin pump use and particular attention will be paid to the following areas:

- Importance of carbohydrate counting and refresher on carbohydrate counting skills
- Understanding insulin to carb ratios and correction factors
- Correct use of bolus calculator - subjects will be required to use this bolus calculator for all insulin boluses during the study period.
- Insulin cartridge and Infusion set changes and correct priming procedure
- Sick day rules
- Dealing with hypo and hyperglycaemia
- Uploading pump data

Written easy to use guidelines for the operation of insulin pump will be provided.

This session will be conducted by a member of the study team and/or a professional pump educator following a written curriculum. Competency in the use of study pump will be assessed.

## **9.4. Training session on the continuous glucose monitoring (Visit 3)**

This session will cover key aspects of the study CGM and particular attention will be paid to the following areas:

- Insertion and initiation of sensor session
- Use of handheld CGM receiver & sensor calibrations
- Use of software to analyse CGM data
- Use of CGM data to optimise treatment
- Uploading CGM data using software

Written guidelines for the operation and use of CGM device will be provided. If necessary, training sessions may be repeated.

This session will be conducted by a member of the study team. Competency in the use of CGM will be assessed.

## **9.5. Run-in period (ends at Visit 4)**

The subject will use study insulin pump and study CGM over the run-in period. The subject will be invited to attend the research centre or contacted via e-mail / telephone at the end of the run-in period. Study insulin pump and CGM device will be downloaded and data may be used for treatment optimisations. There should be a minimum of three weeks run-in period for all subjects (end of Visit 3 to end of Visit 4). Subjects will be able to contact the research team during the run-in period via phone/email to troubleshoot any problems and to ask for any additional training on the devices if required.

At the end of the run-in period (Visit 4), the subject's compliance in using the study CGM and study pump over preceding 14 days will be assessed. To proceed with the study subject needs to demonstrate correct use of study insulin pump including use of bolus calculator over 75% of meal boluses and at least 10 days' worth of CGM data during last 14 days of run-in period.

## **9.6. Randomisation**

Subject will be randomised in Visit 4 if no extension of the run-in period is needed. Eligible subjects will be randomised centrally using a randomisation based on a

computer-generated random code. Randomisation will take place centrally. Subjects will be allocated to either closed-loop intervention preceding sensor augmented insulin pump therapy, or vice versa.

The next section describes the situation when closed-loop precedes the sensor augmented insulin pump therapy.

## **9.7. Closed-loop visit; within 2 weeks of Visit 4 (Visit 5)**

Subject will arrive at the clinical research facility or clinical area at the agreed time. If required this visit can be done remotely by telephone. A blood sample for HbA1c (capillary/venous) will be taken. Subjects will receive training required for safe and effective use of the closed-loop system. This will include training on connection and disconnection of the closed-loop system, and switching between closed-loop and usual pump therapy. Subjects will be advised to use closed-loop 24/7 for the next 4 months with bolus wizard integrated with control algorithm adapted insulin carb ratio for prandial insulin delivery. Written step by step guidance will also be provided, including how to deal with low and high glucose at home. Subjects will be provided with 24 hour telephone helpline and information on when to contact study team. Competency in the use of closed-loop system will be assessed by the study team. Only subjects who demonstrate competency in use of the system will be allowed to continue to the home study phase.

The subject is allowed to drive while adhering to usual precautions and country specific rules and regulations. Subjects will be warned about hypoglycaemia if they start regular exercise during study period.

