1. Non-type 1 diabetes mellitus including those secondary to chronic disease
2. Use of a closed-loop system within the last 30 days
3. Any other physical or psychological disease likely to interfere with the normal conduct of the study and interpretation of the study results as judged by the investigator
4. Commencement of any glucose-lowering agent (such as Pramlintide, Metformin, GLP-1 analogs) in the 3 months prior to enrolment or any use of SGLT2 inhibitors
5. Untreated coeliac disease, adrenal insufficiency or hypothyroidism
6. Known or suspected allergy to insulin
7. More than one episode of severe hypoglycaemia within the last 6 months
8. Random C-peptide  $>200\text{pmol/l}$  with concomitant plasma glucose  $>4\text{ mmol/l}$  (72 mg/dl)
9. Lack of reliable telephone facility for contact
10. Total daily insulin dose  $\geq 2\text{ IU/kg/day}$  or  $< 15\text{ IU/day}$

Maximum duration of study for a subject	44 weeks (11 months)
Recruitment	The subjects will be recruited through the adult diabetes outpatient clinics or other established methods at participating centres.
Consent	Participants will be asked to provide written informed consent.
Baseline Assessment	Eligible subjects will undergo a baseline evaluation including a 12-lead electrocardiogram and blood sample for the measurement of HbA1c, random C-peptide, glucose, renal, liver functions, full blood count, thyroid functions and coeliac antibody screen (if not done in the previous 3 months). Additional centre specific assessments will also be undertaken. Human factors assessment to understand expectations, attitudes, and behaviours that influence the uptake and response to using a closed-loop system will be undertaken at baseline.
Study Training	Training sessions on the use of study CGM, insulin pump (and closed-loop system for those randomised to the intervention group) will be provided by the

	research team (face to face or remotely). Training session on the use of real-time CGM and on how to interpret real-time and retrospective stored data will be provided to all subjects/carers using written material.

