End of study assessments	A blood sample (capillary/venous) will be taken for measurement of HbA1c. Human factor assessment will be performed to understand expectations, attitudes, and behaviours that influence the uptake and response to using a closed-loop system. The human factor assessments include both quantitative and qualitative methods which have been tested in adults in the targeted age range.
Actiwatch application at 2-month of each study period	Subjects will wear an Actiwatch for 7 days for objective sleep quality assessment.
Holter monitor application during the last month of each study period	Subjects will wear a Holter monitor for 5-7 days for retrospective analysis of cardiac rhythm during each study period. Holter monitor data will be analysed at the end of the study. Any incidental finding will be referred by the Investigator to the clinical team and be managed as per local site policy.
Procedures for safety monitoring during trial	
Standard operating procedures for monitoring and reporting of all adverse events and adverse device events will be in place, including serious adverse events (SAE), serious adverse device effects (SADE) and specific adverse events (AE) such as severe hypoglycaemia.
 
A Data Safety and Monitoring Board (DSMB) will be informed of all serious adverse events and any unanticipated adverse device/method effects that occur during the study and will review compiled adverse event data at periodic intervals.

Criteria for withdrawal of patients on safety grounds	
A subject may terminate participation in the study at any time without necessarily giving a reason and without any personal disadvantage. An investigator can stop the participation of a subject after consideration of the benefit/risk ratio. Possible reasons are:
 
 
• Serious adverse events
 
• Significant protocol violation or non-compliance
 
• Failure to satisfy competency assessment
 
• Decision by the investigator, or the sponsor, that termination is in the subject's best medical interest
 
• Allergic reaction to insulin
 
• Technical grounds (e.g. subject relocates)
 

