## **9.19. Participant withdrawal criteria**

The following pre-randomisation withdrawal criteria will apply:

1. Subject is unable to demonstrate safe use of study insulin pump and / or CGM during run-in period as judged by the investigator
2. Subject fails to demonstrate compliance as mentioned in section 9.5 with study insulin pump and / or CGM during run-in period

The following pre- and post-randomisation withdrawal criteria will apply:

3. Subjects may terminate participation in the study at any time without necessarily giving a reason and without any personal disadvantage
4. Significant protocol violation or non-compliance
5. Any severe hypoglycaemia event related to use of the closed-loop system
6. Two severe hypoglycaemia events unrelated to the use of the closed-loop system
7. DKA unrelated to infusion site failure and related to the use of the closed-loop system
8. Decision by the investigator or the sponsor that termination is in the subject's best medical interest

9. Allergic reaction to insulin
10. Severe allergic reaction to adhesive surface of infusion set or glucose sensor

Subjects who are withdrawn for reasons stated in (4) to (10) will be invited to provide a blood sample at the end of the planned study intervention for the assessment of HbA1c.

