42 power, a treatment effect of 10% in the percentage of time in the target range, and a standard
43 deviation of 18% for an individual measurement.

44 **4. Outcome Measures**

45 **Primary Efficacy Endpoint:**

46 • Time spent in the target range (3.9 to 10.0 mmol/L) over the 16 week period

47 **Key Secondary Endpoints:**

48 • Percent time spent with glucose levels above 10.0 mmol/L
49 • HbA1c at 16 weeks
50 • Mean of glucose levels
51 • Percent time spent with glucose levels below 3.9 mmol/L

52 **Secondary Efficacy Endpoints:**

53 *CGM Metrics*

54 Glucose variability

- Standard deviation of glucose levels
- Coefficient of variation of glucose levels

57 Hyperglycemia

- Percent Time spent with glucose levels above 16.7 mmol/L

59 Hypoglycemia

- Percent Time spent with glucose levels below 3.5 mmol/L
- Percent Time spent with glucose levels below 3.0 mmol/L

62 *Insulin Delivery*

- Total insulin dose (units/kg/day)
- Basal insulin dose (units/kg/day)
- Bolus insulin dose (units/kg/day)

66 *Questionnaires*

- WHO-5 quality of life measurement
- Diabetes Distress Scale
- Glucose Monitoring Satisfaction Survey
- Hypoglycemia Confidence
- INSPIRE Survey
- Pittsburgh Sleep Quality Index (PSQI)

73 *Cognitive testing (CogState)*

- Detection Task Score
- Identification Task Score
- One Card Learning Task Score
- One Back Task Score

78 *Actiwatch data*

79 *Holter data*

80 **4.1 Calculation of CGM Metrics**

81 For the primary outcome and all secondary CGM metrics, a single value will be calculated for
82 each subject for each period by pooling all CGM readings between the treatment initiation visit
83 and up to 112 days post-initiation visit or the end of treatment visit, whichever comes first. All
84 glucose sensor readings will be weighted equally in the pooled percentages regardless of how
85 they distribute across weeks. Data will not be truncated due to protocol deviations.

86 Baseline CGM metrics will be calculated by pooling all readings up to the last 14 available days
87 of CGM readings prior to randomization.

88 **5. Analysis Datasets and Sensitivity Analyses**

89

90 **5.1 Analysis Cohorts**

91 The primary analysis and all secondary analyses will be performed on an intention-to-treat basis
92 with each day included in the treatment group assigned by randomization.

93 A per-protocol analysis restricted to randomized participants with a minimum of 60% of

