94 available CGM readings during the control period and 60% CL system use during the CL period
95 will be conducted for the primary outcome.

96 Safety outcomes will be reported for all enrolled participants, regardless of whether the study
97 was completed.

98

99 **6. Analysis of the Primary Endpoint**

100

101 **6.1 Included Subjects**

102 Only subjects with at least 168 hours of CGM data in at least one period will be included. If a
103 subject has more than 168 hours of data in period 1 and then drops out of the study without any
104 data in period 2, then he or she will be included in the analysis.

105 **6.2 Missing Data**

106 Missing data will not be imputed for the primary analysis in this study.

107 **6.3 Statistical Methods**

108 Mean \pm SD or summary statistics appropriate to the distribution will be reported for the primary
109 outcome and each of the key secondary outcomes listed below over the 16 week period by
110 treatment intervention. The treatment interventions will be compared using a linear mixed model
111 adjusting for period as a fixed effect and site as a random effect. The analysis dataset will be
112 three records per subject (one for baseline and one for each period). Inclusion of the pre-
113 randomization baseline value as a third observation for each subject in the model gives a
114 variance reduction analogous to adjusting for it as a covariate. Baseline is not modeled as a
115 covariate in this analysis because there is no corresponding baseline for period 2, only pre-
116 randomization. Note that adjusting for a post-randomization period 2 baseline can introduce a
117 bias so that is not done here. The model will account for correlated data from the same subject.

118 A 95% confidence interval will be reported for the difference between the interventions based on
119 the linear mixed model.

120 Residual values will be examined for an approximate normal distribution. If values are highly
121 skewed, then a ranked normal score transformation will be used instead. However, previous
122 experience suggests that the primary outcome will follow an approximately normal distribution.
123 A two-sided p-value will be reported.

124 For the primary endpoint and other key endpoints listed in section 4, the familywise type I error
125 rate (FWER) will be controlled at two-sided $\alpha = 0.05$. A gatekeeping strategy will be used, where

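### Closed-loop competency is first checked after randomisation, and those who fail give no closed-loop outcome, so the primary analysis is not intention-to-treat for them and their inclusion can depend on allocated sequence

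*Protocol*

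**What the plan says.** **Before randomisation.** Protocol 9.5 and the first two criteria in 9.19 test the study pump and CGM only; the first criterion reads "Subject is unable to demonstrate safe use of study insulin pump and / or CGM during run-in period as judged by the investigator". On timing, Protocol 9.6 says "Subject will be randomised in Visit 4 if no extension of the run-in period is needed".

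**After randomisation.** Closed-loop training and its competency check come at Visit 5. Protocol 9.7 says "Only subjects who demonstrate competency in use of the system will be allowed to continue to the home study phase". In Table 1 (closed-loop first), Visit 5 is at Visit 4 or within two weeks of it. In Table 2 (control first), it follows the control period and washout. Visit 14, which opens the control period, has a sensor-augmented pump competency check but no closed-loop check, and no consequence of failing is stated.

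**What follows a failure.** The synopsis lists "Failure to satisfy competency assessment" among possible reasons for stopping, introduced by "An investigator can stop the participation of a subject after consideration of the benefit/risk ratio", and allows further training. Section 9.19 does not name closed-loop competency failure.

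**Analysis.** SAP 5.1 states intention-to-treat, "with each day included in the treatment group assigned by randomization". SAP 6.1 adds "Only subjects with at least 168 hours of CGM data in at least one period will be included", and SAP 6.2 rules out imputation in the primary analysis.

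**Replacement.** Early first-period drop-outs will be replaced (Protocol 3, six weeks) or may be replaced (Protocol 6, six weeks; 14.6, four weeks).

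**The concern.** Whether a person can learn to operate the closed loop is a response to one of the two treatments. A check on it after randomisation therefore removes outcomes for a treatment-related reason. The closed-loop mean then comes only from people who passed, while the control mean can include some who did not.

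The two sequences also lose different things. A control-first subject who fails has already completed the control period and is kept. A closed-loop-first subject who fails and leaves has only a baseline record, drops out of the primary analysis, and can be replaced by someone new. The same person could thus be counted or not according to the random allocation.

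The trial asks about adults aged 60 and over, in whom difficulty with the device is part of the answer. The per-protocol analysis (Protocol 14.5, SAP 5.1) already addresses competent users through its 60% closed-loop-use criterion, so the primary analysis should not drift towards the same population.

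**Working it through.** **1. Who contributes what under the written rules**

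| Subject who fails at Visit 5 | Baseline | Control | Closed loop | Primary analysis |
|---|---|---|---|---|
| Control first | yes | yes | no | kept, no closed-loop record |
| Closed loop first, goes on to control | yes | yes | no | kept, no closed-loop record |
| Closed loop first, leaves | yes | no | no | excluded by SAP 6.1; may be replaced |

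No row has a closed-loop outcome, and only a closed-loop-first subject can be excluded altogether. One exclusion is 1/36 = 2.8% of those randomised, before any replacement.

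**2. The plan's sample size**

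Inputs (Protocol 14.6, SAP 3): effect 10 points, SD 18 for an individual measurement, 80% power, two-sided 0.05, n = 31.

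For a crossover, n = ((1.960 + 0.842) × SD_diff / 10)², with SD_diff = 18 × √(2(1 − ρ)).

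- ρ = 0.5: SD_diff = 18.0, n = 26.
- ρ = 0.4: SD_diff = 19.7, n = 31.

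The stated 31 therefore needs a within-subject correlation of about 0.4, which the documents do not give. It is under-specified rather than shown to be wrong. I use ρ = 0.4 below.

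**3. Size of the distortion**

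The assumptions are mine: a fraction f fails and gains nothing, and the rest gain the planned 10 points. The effect over all randomised subjects is then 10(1 − f). Failures number 36f, half of them closed-loop first under 1:1 allocation.

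The planned model (baseline, period 1, period 2) was evaluated at its expected value under compound symmetry, omitting site, with closed-loop-first failures leaving. If those who fail have the same control time in range as the others, every record that remains fits a 10-point effect exactly, so the estimate is 10.0. If theirs is 10 to 15 points lower, the estimate rises.

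| f | Failures of 36 | Closed-loop first | All-randomised effect | Model, same control level | Model, 10 to 15 points lower | Overstatement |
|---|---|---|---|---|---|---|
| 5% | 1.8 | 0.9 | 9.5 | 10.0 | 10.1 to 10.2 | 0.5 to 0.7 |
| 10% | 3.6 | 1.8 | 9.0 | 10.0 | 10.2 to 10.3 | 1.0 to 1.3 |
| 15% | 5.4 | 2.7 | 8.5 | 10.0 | 10.3 to 10.5 | 1.5 to 2.0 |

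With ρ = 0.6 the last model column runs from 10.1 to 10.3.

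If closed-loop-first failures go on to control but still give no closed-loop-period data, the estimate at ρ = 0.4 is 10.0 with equal control levels and 10.2 to 11.0 with lower ones. Crossing over alone does not cure the problem; data from the closed-loop period are needed.

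**4. Power if all 36 are analysed as assigned**

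Power = Φ(10(1 − f) / (19.72/√36) − 1.960), where 19.72/6 = 3.29.

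- f = 0: 86%
- f = 5%: 82%
- f = 10%: 78%
- f = 15%: 74%

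**The case against.** A reader might infer four stronger claims that the documents do not support.

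- **That failing ends participation.** Section 9.7 bars entry to the home phase, in a part of the protocol written for the closed-loop-first order. The synopsis makes the stop discretionary and allows further training, and nothing bars a closed-loop-first subject who fails from the control period.
- **That the gate acts in one randomised group.** This is a crossover and both sequences meet it. It is a gate on one treatment.
- **That the analysis loses everyone who could not use the system.** SAP 6.1 keeps control-first failures, and closed-loop-first failures who go on to control. Only those who leave are excluded.
- **That a competency stop forfeits the HbA1c follow-up.** Criterion 8 in 9.19, termination in the subject's best medical interest, could cover it and lies within the group invited for a final sample.

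It is also fair to say that failures may be few. Entrants have used a pump for at least three months, have no severe visual or hearing impairment, and have passed a run-in on the study pump and CGM. Replacement would restore the numbers, and SAP 9.2 already plans flow charts of drop-outs and of subjects eligible for the primary analysis.

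All of this narrows the point but does not remove it. None of it supplies a closed-loop-period outcome for a subject who fails, and replacement restores the count without undoing the selection. Because the text does not settle whether such a subject leaves or goes on to control, sites could handle the same event differently.

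**Conclusion.** The point holds in this form. The closed-loop check comes after randomisation, subjects who fail it give no closed-loop outcome in either sequence, and a closed-loop-first subject who fails and leaves is excluded and replaceable while a control-first one is kept. The primary analysis is therefore not intention-to-treat for these subjects, and inclusion can depend on sequence.

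On assumed failure rates of 5% to 15% with no gain in those who fail, the planned model would overstate the all-randomised effect by about 0.5 to 2.0 points out of 10. The upper end also needs those who fail to have control time in range 15 points below the others. The size rests wholly on these assumptions; if nobody fails, there is no effect. The gap in the rules does not depend on them.

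**What to change.** **Protocol.** Reconcile the synopsis, 9.7 and 9.19 on what follows a failed closed-loop check, including whether the subject may enter the other period. The competency rule and the care of such subjects are for the sponsor to decide. For data purposes, separate not starting closed loop from leaving the study: seek CGM and HbA1c outcomes for both periods from every randomised subject who consents. State that a randomised subject who fails is not replaced in the analysis, and align the replacement wording in sections 3, 6 and 14.6.

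**SAP.**
- In 5.1 and 6.1, analyse any CGM data from that period in the assigned closed-loop arm with 0% closed-loop use. Say whether a failed Visit 5 counts as the treatment initiation visit that starts the window in 4.1.
- Add a sensitivity analysis for those without closed-loop-period data, for example assuming no gain over their control or baseline time in range.
- Show closed-loop competency failures by sequence in the 9.2 flow chart.

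**Cost.** A few sentences in each document and CGM supplies for a small number of subjects. The reported effect would be slightly smaller and some power would be lost: about 78% at 10% failures with 36 analysed and a correlation of 0.4, against the planned 80%.
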